## Phase I/II Study Schema

### 3.1.1 Dose Limiting Toxicity (DLT)

The DLT evaluation window will be the first 28 days of study treatment. No dose reductions or interruptions are allowed during the DLT observation period.

A DLT is defined as any of the following treatment-related toxicities (based on CTCAE Version 5.0):

- Any Grade 5 toxicity, unless due to underlying disease, disease progression, or accidental injury.
- Any Grade  $\geq 3$  non-hematologic toxicity, except:
  - Grade 3 or 4 isolated electrolyte abnormalities that resolve, with or without intervention, to Grade  $\leq 2$  within 72 hours
  - Grade 3 nausea, vomiting, or diarrhea that does not require/prolong hospitalization, does not require TPN or NGT feeding, and resolves to Grade  $\leq 2$  within 72 hours
  - Grade 3 fatigue, fever, flu-like symptoms, or headache lasting  $\leq 72$  hours
  - Grade 3 laboratory abnormalities that are not associated with organ pathology
  - Direct complications of cytopenia(s) due to active myeloid malignancy, such as:
    - Grade 3 or 4 febrile neutropenia
    - Grade 3 or 4 infection
    - Grade 3 or 4 hypotension explained by sepsis
    - Grade 3 or 4 hemorrhage/bleeding
- Confirmed Hy's law cases, defined as:
  - AT (ALT or AST) elevation  $> 3$  times upper limit of normal (ULN), AND
  - Total bilirubin  $> 2$  times ULN, without initial findings of cholestasis (elevated serum alkaline phosphatase), AND

- No other immediately apparent possible causes of AT elevation and hyperbilirubinemia, including, but not limited to, viral hepatitis, pre-existing chronic or acute liver disease, or the administration of other drug(s) known to be hepatotoxic.
- In the absence of active MDS, hematologic DLTs for each arm include:
  - any Grade  $\geq 4$  decrease ANC or PLTs lasting more than 28 days.
- Any adverse reaction that leads to dose reduction or withdrawal of KPT-8602.

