### **3.3 DOSE MODIFICATIONS**

Participants may continue study treatment if toxicity can be managed by interruption of the dose of study treatment or dose reductions as explained below. The following outlines dose modifications for study-drug related toxicities.

If toxicity is considered to be due solely to one of the study drugs as defined below, the participant may be taken off this drug and after consulting with a Sponsor may continue treatment with the other drug only if the participant is deriving benefit from treatment in the form of stabilization of disease or response.

When, at the beginning of a treatment cycle, treatment delay related to one drug is indicated, treatment with the other drug will be continued. For the purpose of restaging, cycle number will continue to be defined on the basis of a time of 28 days (+/- 7 days), i.e., cycle number will not change due to one drug being held.

Overlapping toxicities may be attributed solely to KPT-8602 if a participant who was already on Inqovi prior to starting on study treatment develops the toxicity upon addition of KPT-8602. In addition, overlapping toxicities may be attributed solely to one of the drugs if dose modification or delay of one drug (while the other is continued at the same dose) results in resolution of the toxicity.

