### 3.3.2.2 Toxicity Guidelines

In addition, the tables below show general supportive care and dose modification guidelines for toxicities noted at any point during study treatment (other than the scenarios described above). Dose levels of KPT-8602 and Inqovi for the purposes of toxicity management are as noted in Section 3.3.1.

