### 3.3.2.2.2 Non-hematologic toxicities

Toxicity	Recommended Action*
Fatigue	
Grade 3	
 
• Interrupt KPT-8602 dosing until fatigue improves to Grade <math>\leq</math> 2 or baseline. Maintain dose of Inqovi.
 
• If fatigue does not improve to Grade <math>\leq</math> 2 or baseline within 7 days despite holding KPT-8602, interrupt Inqovi dosing.
 
• Once improved to Grade <math>\leq</math> 2 or baseline:                     
 
○ If first occurrence: restart KPT-8602 and Inqovi at the same dose.
 
○ If second occurrence: restart KPT-8602 one dose level below and Inqovi at same dose.
 
○ If third or later occurrence: restart both KPT-8602 and Inqovi one dose level below.
 
 
 

Unintentional weight loss and anorexia	
Grade 3	
 
• Interrupt KPT-8602 dosing until weight loss/anorexia resolves to Grade <math>\leq</math> 2 or baseline. Maintain dose of Inqovi.
 

Toxicity	Recommended Action*
	
 
• If weight loss/anorexia does not improve to Grade <math>\leq</math> 2 or baseline within 7 days despite holding KPT-8602, interrupt Inqovi dosing.
 
• Once improved to Grade <math>\leq</math> 2 or baseline and participant is clinically stable:                     
 
◦ If first occurrence: restart KPT-8602 one dose level below and Inqovi at the same dose.
 
◦ If second or later occurrence: restart both KPT-8602 and Inqovi one dose level below.
 
 
 
• Provide supportive care, including high-calorie supplements, as needed.
 

Grade 4 (anorexia only)	
 
• Interrupt KPT-8602 and Inqovi dosing until anorexia resolves to Grade <math>\leq</math> 2 or baseline.
 
• Once improved to Grade <math>\leq</math> 2 or baseline, participant is clinically stable, and any other contributing factors have been addressed: restart both KPT-8602 and Inqovi one dose level below.
 
• If anorexia does not improve to Grade <math>\leq</math> 2 or baseline within 7 days, permanently discontinue treatment.
 

Nausea or vomiting, acute	

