Grade 3	
 
• Interrupt KPT-8602 and Inqovi dosing until resolved to Grade <math>\leq</math> 2 or baseline.
 
• Once improved to Grade <math>\leq</math> 2 or baseline and participant is clinically stable:                     
 
◦ If first occurrence and adequate supportive care resulted in improvement to Grade <math>\leq</math> 1 within 3 days: restart KPT-8602 and Inqovi at the current dose
 
◦ If second occurrence or first occurrence not meeting criteria above: restart KPT-8602 one dose level below and Inqovi at same dose.
 
◦ If third occurrence: restart both KPT-8602 and Inqovi one dose level below.
 
 
 

Diarrhea	
Grade 2	
 
• Rule out infectious causes and institute standard anti-diarrheal therapy
 
• After the first occurrence, consider instituting loperamide 2 mg prophylactically approximately 1-2 hours before the administration of KPT-8602 and repeated every 4 hours for the first 12 hours
 
• Reduce KPT-8602 by one dose level until resolved to Grade <math>\leq</math> 1 or baseline, then restart at the current dose level. Maintain Inqovi dose.
 

Grade 3	
 
• Rule out infectious causes and institute standard anti-diarrheal therapy
 
• Institute prophylactic loperamide, as above
 
• Interrupt KPT-8602 and Inqovi until resolved to Grade <math>\leq</math> 1 or baseline.
 
• Once resolved to Grade <math>\leq</math> 1 or baseline:                     
 
◦ If first occurrence: restart KPT-8602 one dose level below and Inqovi at same dose.
 
◦ If second or later occurrence: restart both KPT-8602 and Inqovi one dose level below.
 
◦ If diarrhea stabilizes for at least 4 weeks at Grade <math>\leq</math> 1 or baseline, then the prior dose of KPT-8602 and Inqovi may be resumed at PI discretion.
 
 
 

Grade 4	
 
• Rule out infectious causes and institute standard anti-diarrheal therapy
 
• Institute prophylactic loperamide, as above
 
• Interrupt KPT-8602 and Inqovi until resolved to Grade <math>\leq</math> 1 or baseline.
 
• Once resolved to Grade <math>\leq</math> 1 or baseline: restart both KPT-8602 and Inqovi one dose level below.
 

Hyponatremia	

Toxicity	Recommended Action*

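### Section 3.1.1 bans every dose hold and reduction in the 28-day DLT window, the toxicity tables direct them at any time, and no rule says which governs in Cycle 1

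*Combined protocol and SAP*

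**What the plan says.** Section 3.1.1 sets the DLT window as the first 28 days and states: "No dose reductions or interruptions are allowed during the DLT observation period". It gives no toxicity exception. The same section defines a DLT as any one of several treatment-related events. One bullet covers non-hematologic toxicity of Grade 3 or higher, with listed exemptions. The last bullet covers any adverse reaction that leads to reduction or withdrawal of KPT-8602.

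Section 3.3 takes a different line: "Participants may continue study treatment if toxicity can be managed by interruption of the dose of study treatment or dose reductions as explained below". Section 3.3.2.2 applies its tables to "toxicities noted at any point during study treatment" and sets aside only the scenarios for starting the next cycle. Cycle 1 is not excluded. The rows that matter (Section 3.3.2.2.2) are:

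- Grade 3 fatigue: "Interrupt KPT-8602 dosing until fatigue improves to Grade" 2 or lower, or baseline; then "If first occurrence: restart KPT-8602 and Inqovi at the same dose".
- Grade 3 nausea or vomiting: "Interrupt KPT-8602 and Inqovi dosing until resolved to Grade" 2 or lower, or baseline. A first occurrence restarts at the current dose if supportive care brings it to Grade 1 or lower within 3 days.
- Grade 3 hyponatremia: if sodium is not corrected at once, one KPT-8602 dose is skipped, and dosing resumes at the same level.
- Grade 2 diarrhea: "Reduce KPT-8602 by one dose level until resolved to Grade" 1 or lower, or baseline.
- Grade 3 diarrhea: interrupt both drugs, then "If first occurrence: restart KPT-8602 one dose level below and Inqovi at same dose".

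Section 3.1.2 makes a Cohort 1 participant evaluable for DLT after at least 90% of KPT-8602 doses (9 of 10) and 80% of Inqovi doses (4 of 5), and replaces those not evaluable. Section 3.2.1 extends dosing by a day for each missed dose. It does not mention doses held for toxicity.

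**The concern.** In Cycle 1 an investigator facing one of these events has two instructions that cannot both be followed. The tables recommend a short hold for safety; 3.1.1 prohibits it. Whichever is chosen departs from the other section.

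Two things that feed the 3+3 decision then depend on the choice. The first is evaluability after a hold, because the make-up rule speaks of missed doses only. The second is DLT status where the table directs a reduction. Treatment-related Grade 2 diarrhea is not a DLT if the dose is kept, as the ban requires. It is a DLT under the last bullet if the dose is reduced, as the table directs.

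**Working it through.** **Step 1. Events side by side.** I compare 3.1.1 with the non-hematologic rows of 3.3.2.2.2.

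| Event in Cycle 1 | 3.1.1, by grade | Table action on KPT-8602 | DLT if the table is followed? |
|---|---|---|---|
| Grade 3 fatigue, 72 h or less | Exempt | Hold, same-dose restart | No bullet met |
| Grade 3 nausea/vomiting, meets the exemption and Grade 1 or lower within 3 days | Exempt | Hold, same-dose restart | No bullet met |
| Grade 3 isolated hyponatremia, not corrected at once, Grade 2 or lower within 72 h | Exempt | Skip 1 dose, same level | No bullet met |
| Grade 2 diarrhea | Below Grade 3 | Reduce one level until resolved | Yes, last bullet, if treatment-related |
| Grade 3 diarrhea meeting the exemption | Exempt | Hold, restart one level lower | Yes, last bullet, if treatment-related |

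The first three rows are the clearest conflict: the plan does not count the event as a DLT, yet 3.1.1 forbids the hold that the table directs. In the last two rows, 3.1.1 forbids the reduction and also scores it as a DLT.

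**Step 2. Is precedence stated anywhere?** Sections 3.1, 3.1.1, 3.1.2, 3.3 and 3.3.2.2 were compared. None says that the ban overrides the tables in Cycle 1, or the reverse. The last DLT bullet says how to score a reduction, not whether one may be made.

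**Step 3. Evaluability after a hold.** The plan's figure reproduces: 9/10 = 90%. Planned doses are 10 at levels 1 and -2 (Days 8-12 and 15-19) and 14 at levels 2 and -1 (Days 8-21). The minimum is 90% of planned doses, rounded up: 0.9 × 10 = 9, and 0.9 × 14 = 12.6, so 13.

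| Doses lost and not made up | Levels 1/-2 | Levels 2/-1 |
|---|---|---|
| 1 | 9/10 = 90.0%, passes | 13/14 = 92.9%, passes |
| 2 | 8/10 = 80.0%, fails | 12/14 = 85.7%, fails |
| 3 | 7/10 = 70.0%, fails | 11/14 = 78.6%, fails |

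The one-dose skip for hyponatremia therefore never costs evaluability by itself. A hold of 2 or 3 days starting on a dosing day and not made up fails for 8 of 10 onset days at levels 1/-2 (all but Days 12 and 19) and 13 of 14 at levels 2/-1 (all but Day 21).

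**Step 4. Can held doses be made up inside the window?** Levels 1/-2 leave 28 − 19 = 9 days; levels 2/-1 leave 28 − 21 = 7 days. Three made-up doses end on Day 19 + 3 = 22 or Day 21 + 3 = 24. At levels 2/-1 the 48-hour PK sample falls on Day 23 (Section 5.1). Starting make-up doses on Day 23 after that sample puts three doses on Days 23, 24 and 25. All end by Day 28, so the participant stays evaluable if held doses may be made up.

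**Step 5. Effect on the escalation rule.** If one of the first three participants has treatment-related Grade 2 diarrhea and no other DLT occurs, the count is 0/3 (escalate) when the ban is followed and 1/3 (enter up to 3 more) when the table is followed.

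**The case against.** The best defense is that 3.1.1 is specific and mandatory for one 28-day period, while 3.3.2.2 calls its content guidelines and heads its column as recommended actions. On that reading the specific rule prevails. Lost doses already have a consequence through the 90% and 80% thresholds, with replacement. The sponsor receives the safety data and the criteria met before more participants are enrolled, so a disputed case can surface. Section 3.1.2 also reports no DLTs among 20 patients on single-agent eltanexor given 20 days per cycle.

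Much of this stands as mitigation. It does not supply the missing rule. If the ban prevails, the short hold recommended for safety is prohibited in Cycle 1, and no text says that this is intended. The thresholds decide who is evaluable, not whether a dose may be held.

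A reader might also infer that the last DLT bullet contradicts the exemptions in the same section. The documents do not support that. A DLT is any one of the listed events, and the exemptions qualify only the bullet on Grade 3 or higher non-hematologic toxicity. An event exempt on grade may still be a DLT because it led to a KPT-8602 reduction. That is a defensible conservative rule.

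**Conclusion.** The conflict is real, and the text does not resolve it. It is firmest for the three hold-and-restart events. For table-directed reductions the point is narrower: 3.1.1 forbids them and also counts them as DLTs if treatment-related, so DLT status depends on which section is followed.

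Severity is minor to moderate. Two stronger readings should be resisted:

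- *The plan forces unsafe dosing.* It does not. Sections 3.1 and 3.7.1 allow treatment to stop for toxicity, and 3.7.1 also allows removal at investigator discretion.
- *The conflict will be common.* Section 1.2.3.2 reports any-grade diarrhea in 70%, nausea in 60% and fatigue in 45% of 20 single-agent MDS patients. It gives no Cycle 1 figures and no Grade 2-3 split for these events, so no frequency can be derived.

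The conclusion assumes that a table-directed skipped dose is an interruption within the meaning of 3.1.1. The evaluability failures in Step 3 assume that held doses are not made up.

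**What to change.** 1. Amend 3.1.1 so that the ban covers elective reductions and interruptions only, and state that holds or reductions for toxicity under Section 3.3.2.2 apply in Cycle 1. Cross-reference this in 3.3.2.2.
2. Leave the last DLT bullet unchanged. A treatment-related reaction leading to KPT-8602 reduction or withdrawal stays a DLT; a hold with same-dose restart is not by itself a DLT.
3. State in 3.2.1 that full-dose KPT-8602 doses held for toxicity may be made up within the 28-day window, after the Day 23 PK sample at levels 2/-1, and count toward the 90% threshold.
4. List Cycle 1 toxicity holds and reductions in the escalation report already sent to the sponsor under 3.1.2.

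Carving table-directed reductions out of the last bullet is not advised. Evaluability counts doses, not milligrams. A level 1 participant reduced to 5 mg could take nine or more doses, mostly at 5 mg, and be scored evaluable without DLT at 10 mg. The carve-out would also change which events count toward the Phase II safety pauses in Section 10.4.4.1 (3/9, 4/11 and so on).

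The cost is a few sentences and a cross-reference, with no added visits, procedures or planned participants. A few participants will have a slightly longer Cycle 1 dosing period. With three made-up doses, the days left in the window after the last dose fall from 9 to 28 − 22 = 6 at levels 1/-2, and from 7 to 28 − 25 = 3 at levels 2/-1.

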## 3 STUDY IMPLEMENTATION

### 3.1 STUDY DESIGN

The study consists of two phases:

- Phase I: Safety evaluation with determination of the recommended phase 2 dose (RP2D) of KPT-8602 in combination with Inqovi, and
- Phase II: Efficacy evaluation of KPT-8602 in combination with Inqovi

Participants will be enrolled into one of two cohorts, depending on the phase of study as follows:

- Phase I:
  - **Cohort 1:** Participants with higher-risk MDS that will be treated with Inqovi for 5 days, followed by KPT-8602 at escalating doses.
- Phase II:
  - **Cohort 2:** Participants with higher-risk MDS that will be treated with Inqovi for 5 days, followed by KPT-8602 at the RP2D.

In Phase I, participants enrolled in Cohort 1 will be treated with Inqovi 35 mg/100 mg daily on Days 1-5 of each 28-day cycle, plus KPT-8602 at the corresponding dose level and schedule..

Dose-escalation will follow a standard 3+3 design (see Section [3.1.2](#)), with DLT assessment during the first 28 days of treatment.

In Phase II, participants enrolled in Cohort 2 will be treated with Inqovi 35 mg/100 mg daily on Days 1-5 of each 28-day cycle, plus KPT-8602 at the RP2D identified in Phase I.

The study drugs will be self-administered by the patient, except on days of PK blood draws.

Participants in Cohorts 1 and 2 are eligible to participate in the study if they have received a minimum of 4 cycles of HMA therapy with inadequate response (failure to achieve at least a PR, or experienced disease progression prior to completing 4 cycles). For participants on HMA therapy with Inqovi prior to enrollment, descriptions of initiation of study therapy refer to initiation of KPT-8602 only. Of note, participants receiving Inqovi prior to enrollment must be on the standard dose (35 mg decitabine and 100 mg cedazuridine) without prior dose-reductions.

In both Phase I and Phase II, participants will continue treatment until disease progression, death, unacceptable toxicities as listed in Section [3.3.2](#), or another off-treatment criterion is met (see Section [3.7.1](#)) as long as no other contraindications to further treatment. Participants that do not achieve at least partial remission following cycle 6 will not receive additional treatment.

Blood samples for correlative research will be collected (Section [5.1](#)). Participants may be admitted on day 8 of cycle 1 for pharmacokinetics (PK) studies to be performed, and on other days if necessary or for convenience.

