### 3.1.2 Dose Escalation

In a phase I/II study (NCT 02649790) that evaluated single agent eltanexor in higher-risk MDS, 2 doses were evaluated: 5 patients received 10 mg and 15 patients received 20 mg, every day for 5 days per week of a 28-day cycle. The majority of patients were aged  $\geq 75$  and all were treated and refractory to hypomethylating agents. None of the patients experienced dose-limiting toxicities (DLTs) and the RP2D for eltanexor was selected as 10 mg given on days 1-5 of each week of a 28-day cycle in HR-MDS (20/28 days). Given the overlap in toxicities, particularly hematologic, between hypomethylating agents and eltanexor, our starting dose was set at 10 mg PO daily on Days 8-12 and Days 15-19 (total of 10 days per 28-day cycle as opposed to 20 days per 28-day cycle in NCT 02649790).

In Phase I, dose escalation will proceed in cohorts of 3-6 participants. The MTD is the dose level at which no more than 1 of up to 6 participants experience DLT during the first cycle (28 days) of treatment, and the dose below that at which at least 2 (of  $\leq 6$ ) participants have DLT as a result of the drug.

Participants in Cohort 1 will be eligible for the DLT evaluation if  $\geq 90\%$  (9 out of 10 doses) of KPT-8602 and  $\geq 80\%$  (4 out of 5 doses) of Inqovi were taken within the DLT period. Participants not evaluable for toxicity, will be replaced in the dose level.

Dose Escalation Schedule	
Dose Level	Dose of KPT-8602
Level -2	5 mg PO daily on Days 8-12 and Days 15-19
Level -1	5 mg PO daily on Days 8-21
Level 1 (starting dose)	10 mg PO daily on Days 8-12 and Days 15-19
Level 2	10 mg PO daily on Days 8-21

Dose escalation will start at dose level 1 and follow the rules outlined in the Table below.

Number of Participants with DLT at a Given Dose Level	Escalation Decision Rule
0 out of 3	Enter up to 3 participants at the next dose level
$\geq 2$	Dose escalation will be stopped. This dose level will be declared the maximally administered dose (highest dose administered). Up to three (3) additional participants will be entered at the next lowest dose level if only 3 participants were treated previously at that dose.

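### The one hematologic DLT needs more than 28 days of Grade 4 cytopenia but sits in a 28-day window, and the dose-count rule does not say that a participant held for toxicity is counted

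*Combined protocol and SAP*

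**What the plan says.** **Window.** Section 3.1.1 states: "The DLT evaluation window will be the first 28 days of study treatment". Section 3.1 agrees ("with DLT assessment during the first 28 days of treatment"), and the MTD definition in 3.1.2 counts participants who "experience DLT during the first cycle (28 days) of treatment". For participants already on Inqovi, Section 3.1 adds that "descriptions of initiation of study therapy refer to initiation of KPT-8602 only", so their clock could be taken to start on Day 8.

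**Hematologic item.** It is introduced by "In the absence of active MDS, hematologic DLTs for each arm include" and requires, at Grade 4 or above, a "decrease ANC or PLTs lasting more than 28 days".

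**Catch-all and interruptions.** The DLT list ends with "Any adverse reaction that leads to dose reduction or withdrawal of KPT-8602". The same section says: "No dose reductions or interruptions are allowed during the DLT observation period".

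**Evaluability.** Sections 3.1.2 and 10.2 require at least 90% of KPT-8602 doses (given as 9 of 10) and at least 80% of Inqovi doses (4 of 5) for DLT evaluation. Participants not evaluable for toxicity are replaced. Section 10.3.1 treats everyone as evaluable for toxicity once they have received KPT-8602.

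**Holds.** The tables in 3.3.2.2.1 apply throughout treatment. They call for both drugs to be held for the rest of the cycle in three situations:
- Grade 3-4 thrombocytopenia or Grade 4 neutropenia that has not improved within 72 hours, unless significant marrow disease remains and the physician continues treatment
- Grade 3-4 thrombocytopenia with bleeding
- Grade 3-4 neutropenia with fever

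Each such hold is followed by a one-level KPT-8602 reduction in the next cycle.

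**The concern.** Section 3.1.2 gives overlapping hematologic toxicity as the reason for the reduced starting schedule, yet the DLT written for prolonged cytopenia cannot be reached while DLTs are being counted. The DLT count decides the RP2D, so a listed criterion that cannot contribute to it is a defect in a safety rule.

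The second gap concerns who is in the denominator. A participant taken off KPT-8602 mid-cycle for marrow toxicity can drop below the 90% dose limit. Read literally, the participant is then replaced, although the reason for the missing doses is the toxicity the cohort is meant to detect. In a cohort of three, counting that participant as a DLT gives 1/3 and three more participants at the level. Replacing the participant can give 0/3 and escalation.

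**Working it through.** **The plan's own figures.** The disputed item carries no computed figure. The evaluability fractions are correct for a 10-dose level (9/10 = 90%, 4/5 = 80%). The Phase II pause boundaries in 10.4.4.1, which reuse the DLT definition, also reproduce. With the Beta(1,1) prior and the 0.20 limit, each of the seven listed counts is the smallest whose posterior probability exceeds 0.80 (posteriors from 0.879 to 0.927). The boundaries are not in dispute.

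**Step 1: can the hematologic item be met by Day 28?** Inputs are the 28-day window, a duration of more than 28 days (3.1.1) and KPT-8602 from Day 8 (3.1.2). With onset on day *s* counted as the first day, days observable by Day 28 = 28 - *s* + 1, and the duration is first met on day *s* + 28.

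| Onset day | Days observable by Day 28 | First day met | Days after Day 28 |
|---|---|---|---|
| 1 | 28 | 29 | 1 |
| 8 | 21 | 36 | 8 |
| 15 | 14 | 43 | 15 |
| 28 | 1 | 56 | 28 |

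None of the 28 onset days qualifies by Day 28. Starting the clock at the first KPT-8602 dose gives Days 8-35, and a Day 8 onset qualifies on Day 36, still one day late. In general, an event that arises inside a 28-day window can be seen there for at most 28 days.

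**Step 2: which holds breach the 90% limit?** Doses taken are those scheduled before the hold starts. A rest-of-cycle hold leaves no room to make them up. Levels 1 and -2 have 10 doses (Days 8-12 and 15-19), so 9 are needed. Levels 2 and -1 have 14 (Days 8-21); 0.9 x 14 = 12.6, so 13 are needed.

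| Hold starts | Levels 1, -2 | Levels 2, -1 |
|---|---|---|
| Day 9 | 1/10 | 1/14 |
| Day 15 | 5/10 (50%) | 7/14 (50%) |
| Day 18 | 8/10 (80%) | 10/14 (71.4%) |
| Day 19 | 9/10 (90%, passes) | 11/14 (78.6%) |
| Day 20 | none left to hold | 12/14 (85.7%) |
| Day 21 | none left to hold | 13/14 (92.9%, passes) |

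The limit is breached for holds starting on Days 9-18 and Days 9-20 respectively. A hold from Day 8 precedes any KPT-8602 dose, and replacement is proper there. Isolated missed doses are not the problem: 3.2.1 extends dosing, and 28 - 19 = 9 or 28 - 21 = 7 days are spare.

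**Step 3: how far apart are the two readings?** The documents give no hold rate, so this is illustration only. If each participant has probability *p* of such a hold and there are no other DLTs, a level passes the 3+3 with probability (1-*p*)^3 + 3*p*(1-*p*)^5 when holds count. The result is 0.906, 0.709, 0.494, 0.309 and 0.172 for *p* = 10%, 20%, 30%, 40% and 50%. It is 1.000 throughout if held participants are replaced. This measures the gap between readings and does not estimate bias in this trial.

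**The case against.** The other side has substantial points, and most of them stand.

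- **Follow-up exists.** A reader might infer that nobody tracks the cytopenia past Day 28. The documents do not support that: Sections 6.1 and 8.2 follow adverse events to resolution or stabilization. Section 3.1.2 also makes further enrollment wait for completed DLT evaluation. The duration can therefore become known. What is missing is a statement that it then counts toward Cycle 1 and that the decision waits.
- **Other routes remain.** A reader might infer that no marrow toxicity can be a DLT. That is too strong. Grade 5 events, Grade 3 or worse complications not due to active malignancy, and the catch-all can all capture it.
- **The catch-all probably covers the holds.** Each rest-of-cycle hold leads to a next-cycle reduction, and the catch-all does not require the reduction itself to fall in the window. With 10.3.1, the natural reading is that the participant is counted. It would be wrong to say the plan directs replacement. Still, the 90% rule has no exception for toxicity, and no text ranks the two.
- **Little reach in Cycle 1.** Participants enter with active higher-risk MDS, and the first on-study Phase I marrow, at about C1D28, is worded as something that may be done. Few could be shown to be free of active MDS in the window. Not counting cytopenia during active disease is a legitimate design choice.
- **Phase II.** A reader might infer that the Phase II pause rule is equally disabled. Section 10.4.4.1 states no 28-day limit, so that does not follow. The window there merely needs clarifying.

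**Conclusion.** The concern holds, with narrow reach, and should be fixed. The hematologic DLT cannot operate for dose escalation: it is first met on Day 29 at the earliest, and on Days 36-56 for onsets from the first KPT-8602 dose to Day 28. This rests only on the stated window and duration and on onset at or after Day 1, and it is secure.

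The evaluability gap is an unresolved conflict between rules, not a direction to drop toxic participants. Its arithmetic assumes that 90% applies to the 14-dose levels as 13 of 14 (the text spells out only 9 of 10) and that doses lost to a rest-of-cycle hold are not made up.

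The effect on escalation probability cannot be estimated from the documents. For the hematologic item alone it is probably small, given active MDS at entry. The consequences are also bounded by the single step above the starting level (10 to 14 dosing days per cycle) and by the sponsor's receipt of safety data before further enrollment.

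**What to change.** 1. **Section 3.1.1, hematologic item.** Score it by onset within the window, and hold the cohort decision until counts recover or the required duration is reached. Alternatively, shorten the duration to fit. On its own, more than 14 days captures onsets only to Day 14 (7 of the 21 onset days from Day 8 to Day 28), and more than 7 days only to Day 21 (14 of 21).
2. **Sections 3.1.1 and 3.1.2, counting.** State that an in-window reaction leading to a Cycle 2 reduction or withdrawal of KPT-8602 is a Cycle 1 DLT. State also that a participant who has received KPT-8602 and has a DLT, or misses doses because of treatment-related toxicity, is evaluable and not replaced. Align 10.2 and 10.3.1 with this.

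A sentence in 10.4.4.1 naming the Phase II window would be a useful clarification but is not essential.

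**Cost.** The change is a few sentences by amendment. Under onset scoring, some cohort decisions wait about 8-28 days past Day 28. A level may expand to six more often, adding up to three participants there. Section 3.3.2.1 already requires at least weekly counts for participants without active disease whose counts have not recovered. However, applying the item depends on marrow status, so the sponsor should decide whether the Phase I C1D28 marrow becomes required when this item is in question.
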